## 1 ABBREVIATIONS USED IN THE PROTOCOL

Abbreviation	Term
AE	Adverse event
EHR	Electronic Health Record
FCA	Family Caregiver Application
GCMC	Geisinger Community Medical Center
GHS	Geisinger Health System
GIRB	Geisinger IRB
GMC	Geisinger Medical Center
GWV	Geisinger Wyoming Valley
ID	Identification
IRB	Institutional Review Board
MRN	Medical Record Number
MDC	Multi-Disciplinary Clinic
PA	Pennsylvania
RA	Research Assistant
RedCAP	Research Electronic Data Capture

## **2 BACKGROUND AND SIGNIFICANCE**

### **Cancer Incidence**

Over 1.5 million new cases of cancer will be diagnosed in the United States in 2017 (American Cancer Society, 2017).

### **Family Caregivers**

Family caregivers (or informal caregivers) are people who “provide a complex array of support tasks that extend across physical, psychological, spiritual, and emotional domains” (Honea et al., 2008). Family caregivers perform a multitude of tasks such as picking up prescriptions, assisting with adherence to medical regimens, providing custodial care and nourishment, scheduling medical appointments, transporting patients to and from medical appointments, managing billing and insurance documentation, coping, and emotional and mental stress management. There are an estimated 65 million unpaid family caregivers in the United States (National Alliance for Caregiving & AARP, 2009) that require specific knowledge bases and skills to administer disease-specific care (Given et al., 2008).

### **Cancer and Family Caregivers**

Despite the pivotal role of family caregivers, there are few published studies evaluating interventions with family caregivers and these have been characterized as being of poor quality (Chan et al., 2011). Furthermore, specific to cancer, the National Cancer Institute stated that “family caregivers form the foundation of the health care system in the United States” and that this network and system of caregivers is responsible for supporting many advances in cancer care and likely play a role in the improvement in cancer care and survival seen in the U.S. (National Cancer Institute, 2017).

Much of the focus of existing caregiver interventions in cancer has been on improving knowledge of conditions, symptom management, and caregiver stress management but there has been little attention to a leading contributor to caregiver stress: interaction with the healthcare system. Upon the project team’s review of formative data gathered from patients and caregivers, a major source of experienced stress is the actual coordination of multiple appointments, therapies, scans, and personal lives of patients and their caregivers.

Considering the real-life challenges to care coordination, the Geisinger Innovation Team developed a health information technology solution, called the Family Caregiver Application (“FCA”) to address some of these needs in a thoughtful and meaningful way. FCA is a tool that is shared with patients, caregivers, and medical providers to help coordinate and involve patients and their caregivers as partners in care. Care is not something that is given or done *to* patients, but rather it is a circle of care that envelops the patient and family.

The FCA is a web-based application designed to enhance care coordination and offer benefit across four domains: patient and family satisfaction, quality of care, patient safety, and healthcare system operations. The tool is EHR-agnostic and designed with the ability to consume clinical data and integration with existing functions and patient portals. There is also integration within the EHR for the provider dashboard to use as part of medical encounters and

therapeutic treatments. The tool in its current state is designed for lung cancer however, is extensible to other cancers and other therapeutic areas. Merck Regulatory has reviewed the FCA and determined that it does not meet the criteria for a medical device.

### Patient and Caregiver Satisfaction

While some facets of patient and caregiver stress are very difficult to relieve: the unpredictable effects of a cancer diagnosis, the constant witness to suffering, and the physical and emotional strain that comes with this role, the reduction of uncertainty in the delivery and coordination of care is more amenable to a technological solution. FCA harnesses the power of electronic medical records, scheduling systems, and medication management systems to take some of the uncertainty and feeling of powerlessness out of the delivery of care. Instead of anxiously awaiting a return phone call for scheduling questions, this application is integrated with scheduling information systems (Aria® and Epic®) and electronic medical records so that patients and families (authorized proxies) not only have easy access to this information, but they can also use FCA to securely coordinate personal and medical calendars. This application, unlike others commercially available, *does not* require the manual entry of multiple appointments and medications which steals precious hours from families, rather many of these events and information are virtually *automatically available and automatically updated*.

### Quality of Care

With the ability to better coordinate and more accurately share appointment times, FCA may help to improve overall compliance in combined-modality therapy for lung cancer. The well-coordinated administration of combined-modality therapy in this population is associated with improved clinical outcomes (Curran et al., 2011). With increased patient and caregiver involvement, it is anticipated there will be a reduction in the number of non-planned interruptions in care (as opposed to therapeutic pauses in care for toxicity or other medical issues). This may translate to an improvement in multiple clinically relevant indicators such as compliance with a care plan.

### Patient Safety

Much has been written about the problems with polypharmacy in older patients with cancer (Balducci, 2013). FCA employs a modest medication management tool to assist patients and families in this difficult task. Since patients with lung cancer are frequently seen in oncology outpatient settings, FCA allows patients and caregivers to either post a non-urgent medication question via the tool or make a note (a reminder to themselves) to address a specific question during the next provider encounter.

FCA's provider view allows the clinician access to the medication questions and concerns, so that they may be addressed in the context of the clinical encounter. The provider view of FCA includes a feature in which providers can indicate if they addressed a specific medication question. For urgent issues, patients and their caregivers are directed to call oncology clinics directly to speak with a triage nurse, a medication management pharmacist, or another provider. FCA has an easy-to-use medication scheduling tool which may help to decrease home medication errors.

## Healthcare System Operations

With the pressures to look for efficiencies within the healthcare system, FCA could potentially aid in the triaging of patient and family logistics questions --as compared to questions associated with symptoms or direct medical care. These questions occupy additional patient, caregiver, administrative, and clinician time. In one study, up to 15% of calls to telephone triage were scheduling questions (Flannery, 2009). FCA could potentially free patients, their caregivers, and providers to focus on other domains of concern rather than on scheduling of care.

## **Caregivers: Their value and needs**

Efforts to strengthen the quality of caregiving has had a direct impact on the care of patients. In many instances, the most important determinant of successful healthcare management may be the involvement of an engaged and effective family caregiver. For example, cancer patients were less likely to have unmet needs when family caregivers demonstrated high involvement and effective management (McMullen et al., 2014). Patients are also likely to have unmet needs if the family caregiver burden is high (Deeken et al., 2003). The quality of caregiving may mediate outcomes of interest such as admissions, readmissions, and the ability of the patient to live independently. Enhancing caregiving effectiveness may help to reduce health care costs. For example, an intervention to support family caregivers of patients with dementia could save Minnesota \$996 million in direct care costs over fifteen years (Long et al., 2014).

Family caregivers are demanding technologic solutions to help them perform their roles and communicate with the health care team. FCA potentially responds to this demand with a technological solution that virtually connects the family caregiver, patient, and the healthcare team. **The purpose of this project** is to evaluate how exposure to and use of the FCA may impact quality indicators associated with oncology care, as indicated for advanced lung cancer, among patients, caregivers, and clinicians during a brief, 8-week period.

**Preliminary work:** Several years of work lead to the project team to the exploratory evaluation of FCA. Previous worked occurred in two phases that are described below.

**Application Development - Phase I:** The primary goal of Phase I was to design and build a working prototype. The project team accomplished this as planned by partnering with patients, caregivers and healthcare team members, internally to rapidly conduct market research regarding pain points in managing and performing tasks associated with lung cancer episodes. An external market assessment was also developed. Both efforts informed the design and development of FCA. A Minimally Viable Product (“MVP”) resulted from these efforts.

**Usability Testing - Phase II:** The primary goal of Phase II was to maximize likelihood of commercialization and end-user adoption by ensuring the application was usable and useful. The project team accomplished this as planned by deploying the application in one oncology clinic with twelve (12) patient-caregiver dyads (“Dyads”). Dyads, along with providers in the oncology clinic, provided feedback that was evaluated and translated into application enhancements.

The work conducted under Phase I (#2015-051) and Phase II (#2015-188) was determined to be exempt upon Geisinger Human Research Protection Program review on 04/23/2015 and 12/29/2015, respectively.

## 3 SPECIFIC AIMS

### 3.1 Specific Aim 1

***Observe FCA in clinical oncology practice to evaluate quality and performance indicators.***

Integrate exposure to FCA as standard of care in a conveniently selected clinic for persons with lung cancer and their caregivers. Clinicians in this clinic have contributed to the development and testing of FCA as standard of care at Geisinger Medical Center in Danville, PA (“GMC”). This clinic will serve as the treatment site. Electronic health records and FCA dashboard analytics will be used to evaluate clinician use of the tool. Clinicians at the treatment site will provide interview data describing their experience related to quality, FCA adoption and implementation into workflow integration at the post-period;

### 3.2 Specific Aim 2

***Observe FCA use among patients and caregivers to evaluate quality and performance indicators associated with oncology care.*** From the treatment site, identify, recruit, consent and enroll persons with lung cancer (newly diagnosed or recent recurrence of disease) and their caregivers. Recruitment will continue until 25 patients and 25 caregivers (Case Dyads) are enrolled. Electronic health records for patients (appointment, clinical, and patient-reported data such as the M.D. Anderson Symptom Inventory that is standard of care) and study questionnaires will be used to evaluate quality and performance indicators. Questionnaires will be fielded with Case Dyads, as hereinafter defined, at baseline and after 8 weeks of exposure to FCA. Pre-post changes will be evaluated among cases.

### 3.3 Specific Aim 3

***Observe quality and performance indicators among usual oncology care in similar patient-caregiver population to compare with cases.*** From non-treatment sites, identify, recruit, consent, and enroll persons with lung cancer (newly diagnosed or recent recurrence of disease) and their caregivers into the evaluation study. Recruitment will continue until 25 patients and 25 caregivers are enrolled (Control Dyads). Electronic health records for patients (appointment, clinical, and patient-reported data such as the M.D. Anderson Symptom Inventory that is standard of care) and study questionnaires will be used to evaluate quality and performance indicators however, questionnaires will be fielded at the post-period only. Non-treatment sites will not provide FCA as standard of care and function as control sites. These sites will include Geisinger Wyoming Valley in Wilkes-Barre, PA (“GWV”), and Geisinger Community Medical Center in Scranton, PA (“GCMC”). A case-matched controlled design will be used to evaluate differences in quality and performance indicators between groups at the post-period only.

## 4 STUDY DESIGN

### 4.1 Description

The project team will implement a case-matched controlled design where the Case Dyads, are exposed to the FCA as standard of care in the treatment site and Control Dyads will be exposed to standard of care in the control sites. The study team will collect primary data including study questionnaires from Dyads and interview data from providers; collect secondary operational data (e.g., patient-reported data, FCA analytics, and EHR data; analyze data; interpret results; and disseminate findings in the literature and to study sponsor).

[figure not shown]
This study is characterized as an exploratory evaluation as the design limits the generalizability of findings and these findings will be biased in several ways. First, the treatment clinic and clinicians have been intimately involved in the development and implementation of the FCA. This factor likely influences clinician adoption of the FCA in care and could be limiting factor in other settings where FCA may be tested. Additionally, sites were conveniently chosen and site-level factors may bias study findings. The administration of the study sites is centralized to infer some consistency with operational procedures however this is a limiting factor in this exploratory evaluation. Quality and performance metrics are not routinely collected in these outpatient settings. In the absence of system-level data to describe variation in care, the study will depend on study questionnaires to evaluate quality and performance, which is a limiting factor as the perspective is contained to the study participants rather than the aggregate patient-population at each site. Secondly, a convenient sample of patients receiving care at the study clinics will be recruited into the study on a first-come, first serve basis and without random assignment to treatment or control groups. Additionally, Case Dyads must enroll in MyGeisinger patient portal to use FCA and although not required for the study, we will encourage Control Dyads to enroll in MyGeisinger patient portal to minimize bias related to health literacy using technology. Another potential bias is that some caregivers may reside out of state and this distance may impact the quality of their relationship with the patient; every effort will be made to match Case and Control Dyads with similar spatial situations but this may be prohibitive given the project timeline. These factors limit the assumption that any observations associated with FCA are related to the treatment use as variation in patient factors or the quality of care at clinics may account for observed associations. Potential participants (patients) are reasonably expected to receive an intense, brief oncology care with multiple appointments thus offering the opportunity to measure the impact of FCA use. Dyads will not be randomly assigned to treatment or control but offered standard of care per the clinic site. The study team will provide hands-on technical assistance to Case Dyads and associated clinicians to facilitate implementation and observe key learnings. Changes from baseline to post-study period will be evaluated within the Case Dyads, but given the severity of the condition and brief study period, the project team expects to observe greater differences in post-study period indicators between Case Dyads vs. Control Dyads.

The **first purpose of this project** is to evaluate how **exposure** to FCA may impact quality indicators associated with oncology care, among patients, caregivers, and clinicians during a brief, 8-week period, the project team expects to observe differences in post-period study indicators between

*Version 1.10 – 5.24.2018*

[figure not shown]
CONFIDENTIAL AND PROPRIETARY

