Once appropriate MyGeisinger access has been received, the research assistant will activate the dyad in FCA intervention and provide an overview of FCA's features and functions and answer questions that arise (**Attachment U: RA talking points**). The dyad will be asked to use FCA throughout the course of Oncology Care and provided with technical assistance as needed. The research assistant will assist the dyad with troubleshooting and ask the dyad to confirm that they have at least a basic level of comfort in using FCA.

At the end of the 8-week study period, the dyad will be asked to complete a post-period survey (**Attachment C: Post-Treatment Survey Patient and Attachment D: Post-Treatment Survey Caregiver**) based on their stated format preference determined during consent – in clinic, electronically, or mailed survey. If the Post-Treatment Survey is completed in the clinic, the RA will help to facilitate completion of the survey on an iPad or laptop. If the post-period survey is completed by e-mail or mail, the patient and/or caregiver will receive a letter/email (**Attachment I: Initial Post-Treatment Patient Communication – Case and Attachment J: Version 1.10 – 5.24.2018**

**Initial Post-Treatment Caregiver Communication).** Patients and caregivers will receive unique Surveys. Follow-up will be made in one week to non-responders of the survey (**Attachment K: Reminder- Post Treatment Patient Communication – Case and Attachment L: Reminder – Post Treatment Caregiver Communication – Case**). Three total follow-up attempts will be made to non-responders approximately one week apart; attempts will be made if no data or incomplete data are received with the goal of obtaining completed surveys. Once the study team receives the completed survey, the patient and caregiver will each receive a \$25 gift card. The gift card will be mailed to each individual (**Attachment T: Compensation Letter**).

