The caregiver identified by the patient may not be present for appointments (e.g., caregiver resides out of state). In such cases, enrollment in the study will need to be coordinated over the phone and by email. When this occurs and as possible, the study team will match Case Dyads to Control Dyads who have remote caregivers, but given the logistics of enrolling Case patients, then Case caregivers, matching and recruiting Control patients, and then recruiting Control caregivers in the brief study period, this may be difficult to operationalize and therefore be a source of bias as the Dyads' situations differ by distance. The study staff will ask the patient to speak with the identified caregiver about their interest in participation. Once the study team receives confirmation from the patient, the RA will ask the patient to provide the caregivers name and contact information. The study team will then reach out to the caregiver to explain the study in more detail and determine their interest in participation (**Attachment V: RA Scripts**). The RA will facilitate the applicable MyGeisinger and Proxy Access (**Attachment S: Remote Caregiver Letter**) and send an e-mail to the caregiver to consent and complete the baseline survey (**Attachment G: Initial Recruitment Email Caregiver – Case**). Follow-up will be made in one week if the caregiver has not consented or completed the baseline survey (**Attachment H: Reminder – Pre-Treatment Caregiver Communication – Case**). Three total follow-up attempts will be made to non-responders approximately one week apart; attempts will be made if no data or incomplete data are received with the goal of obtaining completed surveys. Once the study team receives the completed survey, the caregiver will receive a \$25 gift card. The gift card will be mailed to each individual (**Attachment T: Compensation Letter**).

Once consent is obtained, the baseline survey is complete and all applicable MyGeisinger and proxy access has been set up, the RA will call the caregiver to activate them in FCA intervention, offer and provide technical assistance, and confirm that the participating caregiver has at least a basic level of comfort with the FCA (**Attachment V: RA Scripts**)

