### **Control Dyads:**

[figure not shown]
The research assistant will approach all eligible patients in the clinic to inform them of patient-caregiver study (**Attachment U: RA Talking Points**). Interested patients will be asked to identify a caregiver to participate, however patients can participate in the study regardless of caregiver participation. The dyad will provide consent (**Attachment F: Informed Consent – Control**) (eConsent). At the completion of the control participant's 8-week study period, the dyad will complete the post-period survey (**Attachment C – Post Treatment Survey Patient and Attachment D: Post Treatment Survey Caregiver**) based on their stated format

preference determined during consent - in clinic, electronically or mailed (**Attachment O: Initial Post- Treatment Survey Patient Communication – Control** and **Attachment P: Initial Post Treatment Survey Caregiver Communication – Control**). Patients and/or caregivers that do not complete the survey in one week will receive a reminder to complete the survey (**Attachment Q: Reminder- Post Treatment Patient Communication – Control** and **Attachment R: Reminder – Post Treatment Caregiver Communication – Control**). Three total follow-up attempts will be made to non-responders approximately one week apart; attempts will be made if no data or incomplete data are received with the goal of obtaining completed surveys. Once the study team receives the completed survey, the patient and caregiver will each receive a \$25 gift card. The gift card will be mailed to each individual (**Attachment T: Compensation Letter**). Participants who do not receive a copy of their consent form at the time of consent will be mailed a copy of their consent form for their records (**Attachment BB: Consent Form Letter**).

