The caregiver identified by the patient may not be present for appointments (e.g., caregiver resides out of state). In such cases, enrollment in the study will need to be coordinated over the phone and by email. The study staff will ask the patient to speak with the identified caregiver about their interest in participation. If interested, the study team will ask the patient to provide the caregivers name and contact information. The study team will then reach out to the caregiver to explain the study in more detail and determine their interest in participation (**Attachment V: RA Script**). If the caregiver is interested in participating, the RA will explain to the caregiver that they will receive an e-mail to provide their consent to participate (**Attachment M: Initial Recruitment Email Caregiver – Control**). If after one week the caregiver does complete their consent, a reminder will be sent to the participant (**Attachment N: Reminder –Recruitment E-mail Caregiver – Control**). Once the patient reaches the end of their study period, the caregiver will receive request (**Attachment P: Initial Post-Treatment Survey Caregiver Communication – Control**) to complete the survey. In one week, a follow-up will be sent to non-responders (**Attachment R: Reminder – Post Treatment Survey Caregiver Communication – Control**). Three total follow-up attempts will be made to non-responders approximately one week apart; attempts will be made if no data or incomplete data are received with the goal of obtaining completed surveys. Once the study team receives the completed survey, the caregiver will receive a \$25 gift card. The gift card will be mailed to each individual (**Attachment T: Compensation Letter**)

**Providers:** Providers in the treatment site will be asked to participate in a 30-minute interview (**Attachment Y: Physician Interview Guide** with the study team at the post-period. The interview will occur in a private setting either in an office or conference room. Providers will identify the best time to meet with the study team to participate in the interview. Participation will not interfere with the delivery of patient care, perhaps brief one-on-one interviews will be held in parallel or adjacent to regularly scheduled administrative meetings or meal times, strategies that reduce provider burden. In addition to the interview, application metrics and demographic data will be collected on all providers. See section 4.8.1 for more details.

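### The research assistant role that supports FCA for Case Dyads also helps with their in-clinic post-survey, with no stated matching rule for Controls, so survey-based results can be shifted toward FCA

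*Combined protocol and SAP*

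**What the plan says.** Section 4.1 gives Case Dyads and their clinicians direct support: "The study team will provide hands-on technical assistance to Case Dyads and associated clinicians to facilitate implementation and observe key learnings".

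Section 4.5 (Case Dyads) assigns that support to the RA. Once portal access is in place, "the research assistant will activate the dyad in FCA intervention and provide an overview of" its features. During the study, "The research assistant will assist the dyad with troubleshooting". For remote caregivers, "the RA will call the caregiver to activate them in FCA intervention, offer and provide technical assistance".

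The same section then gives the RA a part in collecting the outcome: "If the Post-Treatment Survey is completed in the clinic, the RA will help to facilitate completion of the survey on an iPad or laptop". Case participants who choose e-mail or mail are sent a letter or e-mail, and no RA help is stated for them.

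For Controls, 4.5 says only that at the end of the study period "the dyad will complete the post-period survey", in clinic, electronically or by mail according to the preference given at consent. It does not say whether an RA helps in clinic. Controls meet an RA at recruitment but receive no FCA set-up or support.

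The post-surveys carry satisfaction, quality of life, caregiver burden and coordination of care (4.6). They feed the post-only Case-Control comparison (4.6, 4.8.1) and the Case pre-post comparison (4.7, 4.8.1).

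**The concern.** The survey outcomes are subjective, and the plan describes no blinding. A participant who has been helped by study staff for several weeks, and who then rates care with staff from the same role at hand, may answer more favourably out of courtesy. That would be a fault of measurement. It would arise even if the support had changed nothing about care, so it is a separate matter from whether support counts as part of the exposure.

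Controls have no baseline survey, so a shift in Case post scores passes undiluted into the between-group difference. The Case pre-post change is exposed too: the baseline survey precedes FCA activation, whereas the post-survey follows the support. Section 4.1 names several sources of bias (clinician involvement in development, site, convenience sampling, portal use, caregiver distance) but not this one.

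**Working it through.** **Who does what, side by side (4.5)**

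| Step | Case Dyads | Control Dyads |
|---|---|---|
| FCA set-up, teaching, troubleshooting | RA | None |
| Post-survey in clinic | RA helps on a device | Offered; RA help not specified |
| Post-survey by e-mail or mail | No RA help stated | No RA help stated |
| Private completion or a separate helper required | Not stated | Not stated |

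Mode of completion and presence of a helper are not among the analysis data elements listed in 4.8.1, and no analysis by mode is planned there.

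**The plan's own figure.** Section 4.8.2 says that neither power nor sample size was estimated, so there is no power figure to reproduce. The dyad count in 4.2.1 does reproduce: 153 × 0.5 = 76.5 (77); 77 × 0.37 = 28.5 (28 in the plan); 28 × 0.90 = 25.2 (25).

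**Illustration. Inputs**
- n = 25 dyads per group (3.2, 3.3, 4.2.1).
- Assumed, not in the documents: two-sided 5% t-test; no true FCA effect; equal SDs; shift b of 0.2, 0.3 or 0.5 SD in each assisted Case survey; share s of Case surveys assisted of 0.5 or 1; no shift in Controls.

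**Formulas**
- Shift in the Case mean: Δ = b × s.
- Standard error of the difference: √(2/25) = 0.28 SD.
- Noncentrality: Δ × √(25/2) = 3.54 × Δ, with 48 degrees of freedom. Rejection probability is taken from the noncentral t. The small extra variance when only some surveys are shifted is ignored.

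| b (SD) | s | Δ (SD) | Noncentrality | Rejection |
|---|---|---|---|---|
| 0.2 | 0.5 | 0.10 | 0.35 | 6.4% |
| 0.3 | 0.5 | 0.15 | 0.53 | 8.1% |
| 0.5 | 0.5 | 0.25 | 0.88 | 13.9% |
| 0.2 | 1 | 0.20 | 0.71 | 10.7% |
| 0.3 | 1 | 0.30 | 1.06 | 18.0% |
| 0.5 | 1 | 0.50 | 1.77 | 41.0% |

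With no shift the rate is 5%. If a quarter of Case surveys are assisted, the rates are 5.3%, 5.8% and 7.2%. Section 4.8.2 gives 50 dyads per group, in conflict with the 25 stated elsewhere. At 50 per group the rates would be 7.9%, 11.5% and 23.6% (half assisted) and 16.8%, 31.8% and 69.7% (all assisted).

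**The case against.** The strongest reply is that the wording may describe no more than device help. For the baseline survey, 4.5 has participants complete it on a study iPad through a secure link, and nothing says that the RA reads out items, sees answers or discusses them. The RA talking points and scripts (Attachments U and V) are listed but not reproduced, so they may already contain instructions. This stands as a reason for modesty about size. It does not supply a rule in 4.5.

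The plan also calls the study exploratory and its tests descriptive, and states no 5% threshold. So the rejection rates serve only as a scale for the shift. The described difference would still carry the shift into the sponsor reports and publications foreseen in section 6.

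A reader might infer stronger points that the documents do not support:
- *The same person does both tasks.* Section 4.5 names a role, and 4.3 speaks of research assistants in the plural. Overlap is possible but not stated.
- *Survey help is given in one group only.* This would rest on silence, since Controls may also complete in clinic and the text does not say they do so unaided. The firm asymmetry is the FCA support.
- *It cannot be checked afterwards.* Preferred format is determined at consent in both groups, and hard-copy surveys are tracked in REDCap (4.9.1). Mode is therefore partly recoverable; an RA's presence may not be.
- *The whole primary comparison is affected.* The tables in 4.6 also include missed appointments, admissions, emergency visits, survival and remission from system records, and 4.8.1 says symptom scores are collected in routine practice. None of these passes through the assisted survey.
- *The provider interviews have the same fault.* The plan says "Providers in the treatment site will be asked to participate in a 30-minute interview", conducted by the study team. It does not say that the interviewer is the person who assisted that clinician, and the interviews are qualitative and outside the score comparison.

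**Conclusion.** The point holds in a limited form. The role that supports FCA for Case Dyads also helps with their in-clinic post-surveys. Section 4.5 neither separates the two tasks nor sets a common rule for Controls. Survey-based Case-Control differences and Case pre-post changes can therefore be shifted toward FCA; surveys returned by e-mail or mail and EHR outcomes are not exposed.

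The size cannot be estimated from the documents. Under the assumed shifts of 0.2 to 0.5 SD, the nominal rejection rate is about 6% to 14% if half of Case surveys are assisted and 11% to 41% if all are, against 5% with no shift. Both the size and the direction of the shift are assumptions. The matter is worth settling before surveys are collected, because actual helper presence may not be recoverable later.

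**What to change.** In 4.5, apply one rule to both groups:
- The post-survey is self-completed, by REDCap link, mailed form, or a study device handed to the participant.
- The RA gives help with the device only, and does not view or discuss answers.
- Where a participant needs more help, it comes from an RA who did not support that dyad, if existing staffing allows.
- Actual mode of completion and any helper are recorded for both groups and added to the data elements in 4.8.1.

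In 4.8.1, add a sensitivity analysis that describes the survey results by mode of completion.

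The cost is protocol wording, two data fields and one descriptive table, with no extra staff. The likely downside is a few more incomplete items in clinic, which the three follow-up attempts already planned in 4.5 for incomplete surveys address.
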